1.2.5. BENEFITS AND RISK ASSESSMENT

Although a number of treatment options are available for RA, there remains a clear need for novel therapeutics. Many patients do not benefit optimally from the available small molecule and biologic drugs, leaving opportunity for differentiated drugs with new modes of action and an improved safety profile.

Considering the importance of IL-6 in chronic inflammatory diseases, several companies are developing drugs that target this pathway, and multiple clinical studies have demonstrated that treatment with IL-6 pathway inhibitors can improve

manifestations of RA. ALX-0061, administered i.v. and in combination with MTX, has been shown to be effective in reducing signs and symptoms for the treatment of subjects with active RA.

The current study is designed to evaluate the efficacy and safety of ALX-0061, administered s.c. in subjects with active RA, who have had an inadequate response to methotrexate (subjects from study ALX0061-C201), or who are intolerant to MTX or for whom continued MTX is inappropriate (subjects from study ALX0061-C202). Potential candidates for this study are required to have objective evidence of active disease.

The Sponsor is studying s.c. administration in an effort to develop a route of administration which will offer an alternative and more convenient option for administration, while maintaining its clinical efficacy and safety profile. Details on the design of, and rationale for, the current study are available in section [3.1.1](#) of the protocol.

An assessment of potential risks associated with inhibition of the IL-6 pathway, or inherent to the administration of therapeutic proteins, is described below. IL-6 is a pleiotropic cytokine with an important role in a broad spectrum of biological events, therefore, potential risks related to inhibition of the IL-6 pathway, as well as potential risks inherent to the administration of therapeutic proteins, are considered.

- Inhibition of the IL-6 pathway has immunomodulatory effects, and has been reported to increase the risk for infection [\[15, 16\]](#). So far, serious infections have not been reported for ALX-0061.
- Suppression of IL-6 activity is known to reduce the levels of acute phase proteins such as CRP, SAA and fibrinogen [\[17, 18\]](#).

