 - Rapid and long-lasting decreases in CRP, ESR, fibrinogen and SAA were observed across all ALX-0061 dose groups in study ALX-0061-1.1/10. In general, these pharmacological effects were reversible and associated with clinical response in signs and symptoms of RA.
 - In study ALX0061-C102, results indicate a trend towards a minor decrease in fibrinogen and (hs)CRP levels following administration of ALX-0061 in most subjects.
- Suppression of IL-6 signaling has been shown to lead to decreases in neutrophil and platelet counts [\[19\]](#).
 - In study ALX-0061-1.1/10, a rapid and reversible decrease in neutrophils and platelets was seen in the majority of subjects after administration of ALX-0061. No TEAEs related to the decreases in neutrophil and platelet count (or other hematology parameters) were reported, except for 1 subject with mild leukopenia (without neutropenia; MAD part of the study).

- In study ALX0061-C102, the results show a tendency towards a transient and mild decrease neutrophil count.
- Increased transaminase levels (AST/ALT) in serum and increased cholesterol (HDL, LDL and triglycerides) levels have been reported following pharmacological inhibition of the IL-6 pathway [20]. With the exception of individual subjects showing increases beyond the normal range, there were no clinically relevant trends in mean liver (ALT/AST/GGT/LDH/bilirubin) parameters, mean lipid concentrations, or other safety-related biochemistry parameters across dose levels in study ALX-0061-1.1/10 or ALX0061-C102.
- Recent data indicate that RA subjects have a generally increased rate of gastrointestinal (GI) perforation [21]. At this time, it is not clear whether IL-6 inhibitors further increase the risk of this complication beyond that observed in the general RA population. To date, no cases of GI perforation have been observed following ALX-0061 administration.
- As with all therapeutic proteins used in humans, infusion reactions (e.g., either anaphylactic or anaphylactoid) cannot be excluded.
 - In study ALX-0061-1.1/10, two hypersensitivity reactions were reported (one serious and one moderate). For additional details, please refer to the Investigator's Brochure.
 - In study ALX0061-C102, no hypersensitivity reactions were reported.

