### 4.2 Key Definitions and Labels

#### 4.2.1 *Definition of baseline and change from baseline*

The baseline value will be the baseline value of the parent study.

The absolute change from baseline will be calculated for all post-baseline time points as:  
Change from baseline at time point t = value at time point t – baseline value

For selected efficacy endpoints, the percentage change from baseline will be calculated for all post-baseline time points as: Percentage change from baseline at time point t =  $100 * (value at time point t - baseline value) / baseline value$ . As percentage change can not be calculated for subjects with a baseline value of 0, these subjects will not be included for the corresponding summary analysis (if planned) and the respective column(s) will be kept blank for the corresponding listing.

For the changes from baseline, only subjects with both a baseline value and a value at the post-baseline time point will be included.

Wherever in the document 'change from baseline' is mentioned, it concerns the absolute change from baseline.

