All values will be compared to their matching normal ranges (low, normal, high). For both values and normal ranges the SI units will be considered to determine abnormalities. Additionally, for key hematology and biochemistry parameters, toxicities will be derived according to the common terminology criteria for adverse events (CTCAE, see appendix 16.2) grading, version 4.03 (ALT, AST, total bilirubin, gamma-glutamyltransferase, leukocytes, neutrophils, thrombocytes, fibrinogen and cholesterol). Details for derivation of classification based on normal ranges of laboratory parameters can be found in section 12.4.2.

Cross-tabulations per lab test category (hematology, biochemistry, acute phase proteins, urinalysis, coagulation), lab test and time point will show the shift at each post-baseline time point versus the baseline.

The following types of cross-tabulations will be prepared:

- for all tests with normal ranges: shift in abnormality (L/N/H)
- for ALT, AST, total bilirubin, GGT, leukocytes, neutrophils, thrombocytes, fibrinogen and lipids test results only: shift in CTCAE toxicity grades (grade 1 to 4)

Longitudinal box plots will be prepared for the following variables: neutrophils, platelets, ALT, AST and LDL/HDL ratio.

A detailed list of tables, figures and listings can be found in section 13.4, section 14 and section 15.4, respectively.

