Definition: A finding based on laboratory test results that indicate an increase in levels of creatine phosphokinase in a blood specimen.					

Investigations						
Adverse Event	Grade					
	1	2	3	4	5	
Creatinine Increased	>1 - 1.5 x baseline; >ULN - 1.5 x ULN	>1.5 - 3.0 x baseline; >1.5 - 3.0 x ULN	>3.0 baseline; >3.0 - 6.0 x ULN	>6.0 x ULN	-	
Definition: A finding based on laboratory test results that indicate increased levels of creatinine in a biological specimen.						
Ejection fraction decreased	-	Resting ejection fraction (EF) 50 - 40%; 10 - 19% drop from baseline	Resting ejection fraction (EF) 39 - 20%; >20% drop from baseline	Resting ejection fraction (EF) <20%	-	
Definition: The percentage computed when the amount of blood ejected during a ventricular contraction of the heart is compared to the amount that was present prior to the contraction.						
Electrocardiogram QT corrected interval prolonged	QTc 450 - 480 ms	QTc 481 - 500 ms	QTc >= 501 ms on at least two separate ECGs	QTc >= 501 or >60 ms change from baseline and Torsade de pointes or polymorphic ventricular tachycardia or signs/symptoms of serious arrhythmia	-	
Definition: A finding of a cardiac dysrhythmia characterized by an abnormally long corrected QT interval.						
Fibrinogen decreased	<1.0 - 0.75 x LLN or <25% decrease from baseline	<0.75 - 0.5 x LLN or 25 - <50% decrease from baseline	<0.5 - 0.25 x LLN or 50 - <75% decrease from baseline	<0.25 x LLN or 75% decrease from baseline or absolute value <50 mg/dL	-	
Definition: A finding based on laboratory test results that indicate a decrease in levels of fibrinogen in a blood specimen.						
Forced expiratory volume decreased	FEV1% (percentages of observed FEV1 and FVC related to their respective predicted values) 99 - 70% predicted	FEV1 60 - 69%	50 - 59%	<= 49%	-	
Definition: A finding based on test results that indicate a relative decrease in the fraction of the forced vital capacity that is exhaled in a specific number of seconds.						
GGT Increased	>ULN - 2.5 x ULN	>2.5 - 5.0 x ULN	>5.0 - 20.0 x ULN	>20.0 x ULN	-	
Definition: A finding based on laboratory test results that indicate higher than normal levels of the enzyme gamma-glutamyltransferase in the blood specimen. GGT (gamma-glutamyltransferase) catalyzes the transfer of a gamma glutamyl group from a gamma glutamyl peptide to another peptide, amino acids or water.						

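### Fibrinogen CTCAE grades can be set by a percentage fall from baseline alone, so the expected pharmacological fall is tabulated as toxicity even when the value is not low

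*SAP*

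**What the plan says.** SAP 7.2 (Laboratory Evaluations) plans cross-tabulations "for ALT, AST, total bilirubin, GGT, leukocytes, neutrophils, thrombocytes, fibrinogen and lipids test results only: shift in CTCAE toxicity grades". They appear by visit in Table 14.3.2.4 and as worst case in Table 14.3.2.6. Listing 16.2.8.3 lists every key-parameter result of at least Grade 1, together with the baseline reference.

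The fibrinogen row of SAP Appendix 3 (16.3), presented as CTCAE version 4.03, is:

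- Grade 1: "<1.0 - 0.75 x LLN or <25% decrease from baseline"
- Grade 2: "<0.75 - 0.5 x LLN or 25 - <50% decrease from baseline"
- Grade 3: "<0.5 - 0.25 x LLN or 50 - <75% decrease from baseline"
- Grade 4: "<0.25 x LLN or 75% decrease from baseline or absolute value <50 mg/dL"

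The two arms are joined by an unqualified *or*. SAP 4.2.1 fixes the reference: "The baseline value will be the baseline value of the parent study". SAP 12.4.2 gives derivation rules for low/normal/high status only, and SAP 11 lists no departure from CTCAE.

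Protocol 1.2.5 states that "Suppression of IL-6 activity is known to reduce the levels of acute phase proteins such as CRP, SAA and fibrinogen". It reports such falls in every ALX-0061 dose group of the RA study and adds that in general "these pharmacological effects were reversible and associated with clinical response in signs and symptoms of RA".

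**The concern.** The percentage arm measures how far fibrinogen has moved, not whether it is low. In this trial it is referenced to a value taken before study drug, in active RA, for a protein that the protocol expects the drug to lower. A subject whose raised fibrinogen settles into the normal range therefore meets the criterion for a toxicity grade.

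Nothing in the SAP lets a programmer restrict the percentage arm. Other rows of the same appendix do carry conditions (hemoglobin increased refers to a baseline above ULN, INR to anticoagulation); the fibrinogen row carries none.

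At stake is whether three safety outputs can be read for this parameter. As specified, they do not separate a normalised acute-phase protein from a low fibrinogen. The L/N/H shift is tabulated separately and is not crossed with the grade, so a subject can be normal in one table and Grade 3 in another with nothing to connect the two.

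**Working it through.** The plan states no figure on this point, so there is nothing to reproduce. The check applies the Appendix 3 row literally and compares it with grading on the LLN multiples and the absolute limit alone.

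**Rule.** Literal grade = the higher of the LLN-arm grade and the percentage-arm grade. The 75% in Grade 4 is read as 75% or more.

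**Threshold, with no assumption about levels.** A value v at or above LLN shows a fall of at least c from baseline b when v ≤ b(1 − c). Both conditions can hold only if b ≥ LLN/(1 − c).

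- Grade 2, c = 0.25: b ≥ LLN/0.75 = 1.33 x LLN
- Grade 3, c = 0.50: b ≥ LLN/0.50 = 2 x LLN
- Grade 4, c = 0.75: b ≥ LLN/0.25 = 4 x LLN
- Grade 1: any fall below 25%, so it can occur from any baseline above LLN

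With an **assumed** LLN of 1.5 to 2.0 g/L, the required baselines are 2.0–2.67, 3.0–4.0 and 6.0–8.0 g/L for Grades 2, 3 and 4.

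**Worked cases (assumed LLN 2.0 g/L).**

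| Baseline | Fall | Value | Below LLN? | Literal grade | LLN multiples only |
|---|---|---|---|---|---|
| 5.0 | 10% | 4.5 | no | 1 | 0 |
| 5.0 | 30% | 3.5 | no | 2 | 0 |
| 5.0 | 50% | 2.5 | no | 3 | 0 |
| 5.0 | 75% | 1.25 | yes (0.625 x LLN) | 4 | 2 |
| 8.0 | 75% | 2.0 | no (at LLN) | 4 | 0 |
| 4.5 | 60% | 1.8 | yes (0.9 x LLN) | 3 | 1 |

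If the upper limit is taken as 4.0 g/L, the first row is graded as decreased while still above the normal range. At baseline itself the percentage arm cannot apply, so a subject with normal or high fibrinogen starts ungraded and any later fall appears as a worsening shift.

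**Illustrative frequency at one visit.** All inputs are assumed: 400,000 draws, baseline mean 4.5 g/L (SD 1.1), LLN 2.0 g/L, mean fall 35, 45 or 55% (SD 15 points).

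| Result at mean fall of | 35% | 45% | 55% |
|---|---|---|---|
| Grade ≥1, literal | 99% | ~100% | ~100% |
| Grade ≥1, LLN multiples only | 18% | 33% | 52% |
| Grade ≥3, literal | 16% | 37% | 63% |
| Grade ≥3, percentage arm kept only below LLN | ~10% | 24% | 46% |
| Grade ≥3, LLN multiples only | 1% | 3.5% | 10% |
| Share of literal Grade ≥3 at or above LLN | 41% | 35% | 27% |

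Varying LLN over 1.5–2.0 g/L and the baseline mean over 4–5 g/L moves the last row between 17% and 85%. Literal Grade ≥1 stays at about 99–100%.

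**The case against.** The strongest defence is that the SAP uses a named, published scale as it stands, and Protocol 3.5.1.1 also points to CTCAE for the severity of laboratory abnormalities. Removing a criterion for one safety parameter lowers its grades, which is a judgement that needs justifying. The row is not shown to be mistranscribed. This stands, and it is why the change must be disclosed.

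The other laboratory outputs also help. Tables 14.3.2.3 and 14.3.2.5 give L/N/H by visit and worst case, Listing 16.2.8.2 is restricted to out-of-range or clinically significant results, and Table 14.3.2.1 gives values and changes. A reader might infer that true low-fibrinogen cases would be lost, or that the safety conclusion would be wrong. The documents do not support that: low values remain identifiable, the analysis is descriptive, the investigator assesses clinical relevance, and fibrinogen is not among the laboratory discontinuation criteria. Nor do the two kinds of table contradict each other; they answer different questions. But none of this alters what the CTCAE tables would show.

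A reader might also infer that Grade 4 would often be assigned to normal values. It needs a baseline of at least 4 x LLN. In the base simulation, most literal Grade ≥3 values (59–73%) are below LLN.

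Finally, the assumed falls of 35–55% have no source in the documents. The single-dose healthy-volunteer study is described as showing only a minor or mild decrease, though that is a different population and regimen. The frequencies cannot be read as predictions.

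**Conclusion.** The point holds on the text. Literal use of the Appendix 3 row grades any fall in fibrinogen as at least Grade 1, and a value that is not low as Grade 2 from a baseline of 1.33 x LLN or Grade 3 from 2 x LLN. These thresholds follow from the row alone.

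Since the protocol expects fibrinogen to fall on treatment, nearly every treated subject could carry a grade. Tables 14.3.2.4 and 14.3.2.6 and Listing 16.2.8.3 would then mix normalisation with low fibrinogen. How many subjects would reach Grade 2 or 3 with a normal value cannot be derived, because fibrinogen levels, LLN and size of fall are not given.

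The consequence is three outputs that are hard to interpret for one parameter, not a loss of the information on low values. The documents support calling the fall an expected pharmacological effect; they do not call it an intended one. The correction is worth making before the tables are programmed.

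**What to change.** State one rule in SAP 7.2 and Appendix 3: in Tables 14.3.2.4 and 14.3.2.6 and Listing 16.2.8.3, fibrinogen is graded on the LLN multiples and the absolute limit (<50 mg/dL) only. Footnote the departure from the CTCAE 4.03 row in each output. The percentage fall can be shown separately; the absolute change is already in Table 14.3.2.1.

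Do not treat keeping the percentage arm for values below LLN as the same rule. The fall from 4.5 to 1.8 g/L is Grade 1 under the proposed rule and Grade 3 under that alternative, and in the illustration the alternative retains well over half of the literal Grade ≥3 results.

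If the literal CTCAE row must be kept, cross the fibrinogen grade with L/N/H status in the same tables.

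While editing SAP 7.2, correct its CTCAE cross-reference: it points to Appendix 16.2 (the prednisolone chart), but the grades are in 16.3.

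The cost is one sentence, one derivation rule and a footnote, with no new data. The small downside is that one parameter departs from the literal CTCAE text.

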## 16.4 Appendix 4: FACIT-F Scoring Guidelines (version 4)

- Instructions:\*
1. Record answers in "item response" column. If missing, mark with an X
  2. Perform reversals as indicated, and sum individual items to obtain a score.
  3. Multiply the sum of the item scores by the number of items in the subscale, then divide by the  
number of items answered. This produces the subscale score.
  4. Add subscale scores to derive total scores (TOI, FACT-G & FACIT-F).
  - 5. The higher the score, the better the QOL.**

Subscale	Item Code	Reverse item?	Item response	Item Score
PHYSICAL	GP1 =_____	4	-	_____
WELL-BEING (PWB)	GP2 =_____	4	-	_____
	GP3 =_____	4	-	_____
	GP4 =_____	4	-	_____
Score range: 0-28	GP5 =_____	4	-	_____
	GP6 =_____	4	-	_____
	GP7 =_____	4	-	_____
Sum individual item scores: _____				
Multiply by 7: _____				
Divide by number of items answered:				
=PWB subscale score				

SOCIAL/FAMILY	GS1	0	+	_____	=_____
WELL-BEING (SWB)	GS2 GS3 GS4	0 0 0	+	_____	=_____
	GS5 GS6	0 0	+	_____	=_____
Score range: 0-28					

$$\text{GS7} \quad 0 \quad + \quad \underline{\quad} \quad = \underline{\quad}$$

*Sum individual item scores:* \_\_\_\_\_  
*Multiply by 7:* \_\_\_\_\_  
*Divide by number of items answered:* \_\_\_\_\_

EMOTIONAL	GE1	4	-	_____	= _____
WELL-BEING	GE2	0	+	_____	= _____
(EWB)	GE3	4	-	_____	= _____
	GE4	4	-	_____	= _____
Score range: 0-24	GE5	4	-	_____	= _____
	GE6	4	-	_____	= _____

		Sum individual item scores: _____		
		Multiply by 6: _____		
		Divide	by	number of items answered:
_____	=EWB subscale score			
FUNCTIONAL	GF1	0	+	_____ = _____
WELL-BEING	GF2	0	+	_____ = _____
(FWB)	GF3	0	+	_____ = _____
	GF4	0	+	_____ = _____
Score range: 0-28	GF5	0	+	_____ = _____
	GF6	0	+	_____ = _____
	GF7	0	+	_____ = _____

*Sum individual item scores:* \_\_\_\_\_  
*Multiply by 7:* \_\_\_\_\_  
*Divide by number of items answered:* \_\_\_\_\_  
\_\_\_\_\_ =FWB subscale score

Subscale Score	Item Code	Reverse item?	Item response	Item
-----------------------	------------------	----------------------	----------------------	-------------

FATIGUE	HI7	4	-	_____	= _____
SUBSCALE	HI12	4	-	_____	= _____
(FS)	An1	4	-	_____	= _____
	An2	4	-	_____	= _____
Score range: 0-52	An3	4	-	_____	= _____
	An4	4	-	_____	= _____
	An5	0	+	_____	= _____
	An7	0	+	_____	= _____
	An8	4	-	_____	= _____
	An12	4	-	_____	= _____
	An14	4	-	_____	= _____
	An15	4	-	_____	= _____
	An16	4	-	_____	= _____

*Sum individual item scores: \_\_\_\_\_*

*Multiply by 13: \_\_\_\_\_*

*Divide by number of items answered: \_\_\_\_\_ =F*

**Subscale score**

**To derive a FACIT-F Trial Outcome Index (TOI):**

Score range: 0-108

$$= \frac{\text{_____}}{(\text{PWB score})} + \frac{\text{_____}}{(\text{FWB score})} + \frac{\text{_____}}{(\text{FS score})} = \text{FACIT-F TOI}$$

**To Derive a FACT-G total score:**

Score range: 0-108

$$= \frac{\text{_____}}{(\text{PWB score})} + \frac{\text{_____}}{(\text{SWB score})} + \frac{\text{_____}}{(\text{EWB score})} + \frac{\text{_____}}{(\text{FWB score})} = \text{FACT-G Total score}$$

**To Derive a FACIT-F total score:**

Score range: 0-

100

$$= \underline{\quad} + \underline{\quad} + \underline{\quad} + \underline{\quad} + \underline{\quad} \\ \text{=FACIT-F Total score} \\ (\text{PWB score}) (\text{SWB score}) (\text{EWB score}) (\text{FWB score}) (\text{FS score})$$

\*For guidelines on handling missing data and scoring options, please refer to the Administration and Scoring Guidelines in the manual or on-line at [www.facit.org](http://www.facit.org).

## 16.5 Appendix 5: Search criteria for adverse events of special interest

Search criteria for AESIs are either MedDRA PT clusters or SMQs. The SMQs and the individual PTs for the PT clusters are provided below. The MedDRA version used for the data coding is v21.0.

### Infections

Abdominal abscess	Acarodermatitis	Acute sinusitis
Abdominal hernia gangrenous	Acid fast bacilli infection	Adenoiditis
Abdominal infection	Acinetobacter bacteraemia	Adenopathy syphilitic
Abdominal lymphadenopathy	Acinetobacter infection	Adenoviral conjunctivitis
Abdominal sepsis	Acinetobacter test positive	Adenoviral haemorrhagic cystitis
Abdominal wall abscess	Acne pustular	Adenoviral hepatitis
Abdominal wall infection	Acquired immunodeficiency syndrome	Adenoviral upper respiratory infection
Abortion infected	Acrodermatitis chronica atrophicans	Adenovirus encephalomyeloradiculitis
Abscess	Actinomyces test positive	Adenovirus infection
Abscess bacterial	Actinomycosis	Adenovirus test
Abscess fungal	Actinomycotic abdominal infection	Adenovirus test positive
Abscess intestinal	Actinomycotic pulmonary infection	Adiponectin increased
Abscess jaw	Actinomycotic skin infection	Administration site abscess
Abscess limb	Acute endocarditis	Administration site cellulitis
Abscess neck	Acute focal bacterial nephritis	Administration site infection
Abscess of external auditory meatus	Acute haemorrhagic conjunctivitis	Adrenal gland abscess
Abscess of eyelid	Acute hepatitis B	Adrenal gland tuberculosis
Abscess of salivary gland	Acute hepatitis C	Adrenalitis
Abscess oral	Acute HIV infection	Aeromonas infection
Abscess rupture	Acute pulmonary histoplasmosis	Aeromonas test positive
Abscess soft tissue		African trypanosomiasis
Abscess sweat gland		AIDS cholangiopathy
Acanthamoeba infection		
Acanthamoeba keratitis		
Acariasis		

AIDS related complex	Angina gangrenous	Application site folliculitis
AIDS related complication	Angiostrongylus infection	Application site infection
AIDS retinopathy	Anicteric leptospirosis	Application site pustules
Air-borne transmission	Anisakiasis	Arachnoiditis
Alcaligenes infection	Anogenital warts	Arboviral infection
Allescheriosis	Anorectal cellulitis	Arbovirus test positive
Alopecia syphilitic	Anorectal human papilloma virus infection	Arenaviral haemorrhagic fever
Alpha haemolytic streptococcal infection	Anorectal infection	Arenavirus test positive
Alphaviral infection	Anorectal infection bacterial	Argentine haemorrhagic fever
Alphavirus test	Anthrax	Arteriosclerotic gangrene
Alphavirus test positive	Anthrax sepsis	Arteriovenous fistula site infection
Alternaria infection	Antifungal treatment	Arteriovenous graft site abscess
Alveolar osteitis	Antimicrobial susceptibility test	Arteriovenous graft site infection
American trypanosomiasis	Antimicrobial susceptibility test intermediate	Arteritis infective
Amniotic cavity infection	Antimicrobial susceptibility test resistant	Arthritis bacterial
Amniotic infection syndrome of Blane	Antimicrobial susceptibility test sensitive	Arthritis fungal
Amoeba test	Aortic aneurysm syphilitic	Arthritis gonococcal
Amoeba test positive	Aortitis salmonella	Arthritis helminthic
Amoebiasis	Aortitis syphilitic	Arthritis infective
Amoebic brain abscess	Aphthovirus test positive	Arthritis reactive
Amoebic colitis	Apical granuloma	Arthritis rubella
Amoebic dysentery	Appendiceal abscess	Arthritis salmonella
Amoebic lung abscess	Appendicitis	Arthritis viral
Amoebic skin ulcer	Appendicitis perforated	Arthropod infestation
Anal abscess	Application site abscess	Arthropod-borne disease
Anal candidiasis	Application site cellulitis	Ascariasis
Anal chlamydia infection		Aspergilloma
Anal fistula infection		Aspergillosis oral
Anal fungal infection		
Anal infection		
Anal tinea		

Aspergillus infection	Bacterial disease carrier	Bifidobacterium infection
Aspergillus test	Bacterial food poisoning	Bifidobacterium test positive
Aspergillus test positive	Bacterial infection	Bile culture
Astrovirus test positive	Bacterial iritis	Bile culture positive
Asymptomatic bacteriuria	Bacterial labyrinthitis	Biliary abscess
Asymptomatic HIV infection	Bacterial pericarditis	Biliary sepsis
Asymptomatic viral hepatitis	Bacterial prostatitis	Biliary tract infection
Atypical mycobacterial infection	Bacterial pyelonephritis	Biliary tract infection bacterial
Atypical mycobacterial lower respiratory tract infection	Bacterial rhinitis	Biliary tract infection cryptosporidial
Atypical mycobacterial lymphadenitis	Bacterial sepsis	Biliary tract infection fungal
Atypical mycobacterial pneumonia	Bacterial test	Biliary tract infection helminthic
Atypical mycobacterium pericarditis	Bacterial test positive	Biliary tract infection viral
Atypical mycobacterium test positive	Bacterial toxæmia	BK virus infection
Atypical pneumonia	Bacterial tracheitis	Black piedra
Avian influenza	Bacterial translocation	Bladder candidiasis
Babesiosis	Bacterial vaginosis	Bladder diverticulitis
Bacillary angiomatosis	Bacterial vulvovaginitis	Blastocystis infection
Bacillus bacteraemia	Bacteriuria	Blastomycosis
Bacillus infection	Bacteriuria in pregnancy	Blebitis
Bacillus test positive	Bacteroides bacteraemia	Blepharitis
Bacteraemia	Bacteroides infection	Blister infected
Bacterascites	Bacteroides test positive	Blood bactericidal activity
Bacterial abscess central nervous system	Balamuthia infection	Blood beta-D-glucan abnormal
Bacterial allergy	Balanitis candida	Blood beta-D-glucan decreased
Bacterial dacryocystitis	Balanoposthitis	Blood beta-D-glucan increased
Bacterial diarrhoea	Balanoposthitis infective	Blood culture
	Balantidiasis	Blood culture positive
	Bartholin's abscess	
	Bartonella test positive	
	Bartonellosis	
	Bed bug infestation	
	Beta haemolytic streptococcal infection	

Blood HIV RNA	Bronchitis haemophilus	Campylobacter gastroenteritis
Blood HIV RNA below assay limit	Bronchitis moraxella	Campylobacter infection
Blood HIV RNA decreased	Bronchitis pneumococcal	Campylobacter sepsis
Blood HIV RNA increased	Bronchitis viral	Campylobacter test positive
Body tinea	Bronchoalveolar lavage abnormal	Candida cervicitis
Bolivian haemorrhagic fever	Bronchopulmonary aspergillosis	Candida endophthalmitis
Bone abscess	Bronchopulmonary aspergillosis allergic	Candida infection
Bone tuberculosis	Bronchoscopy abnormal	Candida nappy rash
Borderline leprosy	Brucella sepsis	Candida osteomyelitis
Bordetella infection	Brucella test	Candida pneumonia
Bordetella test	Brucella test positive	Candida retinitis
Bordetella test positive	Brucellosis	Candida sepsis
Borrelia infection	Bubonic plague	Candida test
Borrelia test	Bulbar poliomyelitis	Candida test positive
Borrelia test positive	Bullous impetigo	Candiduria
Botryomycosis	Burkholderia cepacia complex infection	Capillariasis
Botulism	Burkholderia cepacia complex sepsis	Capillaritis
Boutonneuse fever	Burkholderia gladioli infection	Capnocytophaga infection
Bovine pustular stomatitis virus infection	Burkholderia infection	Capnocytophaga test positive
Bovine tuberculosis	Burkholderia mallei infection	Carbuncle
Brain abscess	Burkholderia pseudomallei infection	Cardiac granuloma
Brain empyema	Burkholderia test positive	Cardiac infection
Breast abscess	Burn infection	Cardiac valve abscess
Breast cellulitis	Bursitis infective	Cardiac valve vegetation
Breast discharge infected	Bursitis infective staphylococcal	Cardiovascular syphilis
Bronchiectasis	Calicivirus test positive	Carditis
Bronchiolitis		Cat scratch disease
Bronchitis		Catheter culture
Bronchitis bacterial		Catheter culture positive
Bronchitis fungal		Catheter site abscess

Catheter site cellulitis	Cervicitis gonococcal	Chronic recurrent multifocal osteomyelitis
Catheter site infection	Cervicitis human papilloma virus	Chronic sinusitis
Catheter site pustule	Cervicitis mycoplasmal	Chronic tonsillitis
Catheter site warmth	Cervicitis streptococcal	Citrobacter infection
Cavernous sinus thrombosis	Cervicitis trichomonal	Citrobacter sepsis
Cellulitis	Cervix warts	Citrobacter test positive
Cellulitis enterococcal	Cestode infection	Clitoris abscess
Cellulitis gangrenous	Chancroid	Clonorchiasis
Cellulitis laryngeal	Chest wall abscess	Clostridial infection
Cellulitis of male external genital organ	Chikungunya virus infection	Clostridial sepsis
Cellulitis orbital	Chlamydia test	Clostridium bacteraemia
Cellulitis pasteurella	Chlamydia test positive	Clostridium colitis
Cellulitis pharyngeal	Chlamydial cervicitis	Clostridium difficile colitis
Cellulitis staphylococcal	Chlamydial infection	Clostridium difficile infection
Cellulitis streptococcal	Chlamydial pelvic inflammatory disease	Clostridium test
Central nervous system abscess	Cholangitis infective	Clostridium test positive
Central nervous system enteroviral infection	Cholecystitis infective	CNS ventriculitis
Central nervous system fungal infection	Cholera	Coccidioides encephalitis
Central nervous system infection	Cholesteatoma	Coccidioidomycosis
Central nervous system inflammation	Cholesterol granuloma	Colitis herpes
Central nervous system viral infection	Choriomeningitis lymphocytic	Colon gangrene
Cerebral aneurysm ruptured syphilitic	Chorioretinitis	Colonic abscess
Cerebral aspergillosis	Choroid tubercles	Colorado tick fever
Cerebral fungal infection	Choroiditis	Colorado tick fever virus test positive
Cerebral malaria	Chromoblastomycosis	Colostomy infection
Cerebral septic infarct	Chronic gastritis	Community acquired infection
Cerebral toxoplasmosis	Chronic hepatitis	Condyloma latum
Cervicitis	Chronic hepatitis B	Congenital condyloma
	Chronic hepatitis C	
	Chronic pulmonary histoplasmosis	

Congenital cytomegalovirus infection	Corona virus infection	Cryptococcosis
Congenital hepatitis B infection	Coronavirus test positive	Cryptococcus test
Congenital herpes simplex infection	Corynebacterium infection	Cryptococcus test positive
Congenital HIV infection	Corynebacterium sepsis	Cryptosporidiosis infection
Congenital infection	Corynebacterium test	CSF culture
Congenital malaria	Corynebacterium test positive	CSF culture positive
Congenital pneumonia	Cow pox	CSF immunoglobulin G index
Congenital rubella infection	Coxiella infection	CSF
Congenital syphilis	Coxiella test positive	leukocyte/erythrocyte ratio
Congenital syphilitic encephalitis	Coxsackie carditis	CSF
Congenital syphilitic meningitis	Coxsackie endocarditis	leukocyte/erythrocyte ratio increased
Congenital syphilitic osteochondritis	Coxsackie myocarditis	CSF measles antibody positive
Congenital toxoplasmosis	Coxsackie pericarditis	CSF virus identified
Congenital tuberculosis	Coxsackie viral disease of the newborn	CSF virus no organisms observed
Congenital varicella infection	Coxsackie viral infection	Culture
Congo-Crimean haemorrhagic fever	Coxsackie virus test	Culture cervix
Conjunctivitis	Coxsackie virus test positive	Culture cervix positive
Conjunctivitis bacterial	Cranial nerve infection	Culture positive
Conjunctivitis chlamydial	Creutzfeldt-Jakob disease	Culture stool
Conjunctivitis gonococcal neonatal	Cronobacter bacteraemia	Culture stool positive
Conjunctivitis tuberculous	Cronobacter infection	Culture throat
Conjunctivitis viral	Cronobacter necrotising enterocolitis	Culture throat positive
Corneal abscess	Cronobacter test positive	Culture tissue specimen
Corneal endotheliitis	Cross infection	Culture tissue specimen positive
Corneal infection	Croup infectious	Culture urine
	Cryptococcal cutaneous infection	Culture urine positive
	Cryptococcal fungaemia	Culture wound
		Culture wound positive
		Cutaneous anthrax

Cutaneous coccidioidomycosis	Cytomegalovirus gastroenteritis	Dental fistula
Cutaneous larva migrans	Cytomegalovirus gastrointestinal infection	Dental gangrene
Cutaneous leishmaniasis	Cytomegalovirus hepatitis	Dermatitis infected
Cutaneous sporotrichosis	Cytomegalovirus infection	Dermatomyositis
Cutaneous tuberculosis	Cytomegalovirus mononucleosis	Dermatophytosis
Cyclitis	Cytomegalovirus mucocutaneous ulcer	Dermo-hypodermitis
Cyclosporidium infection	Cytomegalovirus myelomeningoradiculitis	Device related infection
Cystitis	Cytomegalovirus myocarditis	Device related sepsis
Cystitis bacterial	Cytomegalovirus oesophagitis	Diabetic foot infection
Cystitis erosive	Cytomegalovirus pancreatitis	Diabetic gangrene
Cystitis escherichia	Cytomegalovirus pericarditis	Diaphragmatic hernia gangrenous
Cystitis glandularis	Cytomegalovirus syndrome	Diarrhoea infectious
Cystitis gonococcal	Cytomegalovirus test	Diarrhoea infectious neonatal
Cystitis haemorrhagic	Cytomegalovirus test positive	Diphtheria
Cystitis helminthic	Cytomegalovirus urinary tract infection	Diphtheria carrier
Cystitis interstitial	Cytomegalovirus viraemia	Diphyllobothriasis
Cystitis klebsiella	Dacryoadenitis acquired	Direct infection transmission
Cystitis noninfective	Dacryocanaliculitis	Disseminated cryptococcosis
Cystitis pseudomonal	Dacryocystitis	Disseminated cytomegaloviral infection
Cystitis radiation	Deltaretrovirus test positive	Disseminated tuberculosis
Cystitis ulcerative	Demodicidosis	Diverticulitis
Cystitis viral	Dengue fever	Douglas' abscess
Cytomegalovirus chorioretinitis	Dental caries	Dracunculiasis
Cytomegalovirus colitis		Dural abscess
Cytomegalovirus duodenitis		Dysentery
Cytomegalovirus enteritis		Ear infection
Cytomegalovirus enterocolitis		Ear infection bacterial
Cytomegalovirus gastritis		Ear infection fungal

Ear infection staphylococcal	Encephalitis brain stem	Endocarditis enterococcal
Ear infection viral	Encephalitis california	Endocarditis gonococcal
Ear lobe infection	Encephalitis cytomegalovirus	Endocarditis haemophilus
Ear tuberculosis	Encephalitis eastern equine	Endocarditis helminthic
Ebola disease	Encephalitis enteroviral	Endocarditis histoplasma
Ebola Reston virus infection	Encephalitis fungal	Endocarditis meningococcal
Ebola virus test positive	Encephalitis haemorrhagic	Endocarditis pseudomonal
Echinococcosis	Encephalitis influenzal	Endocarditis Q fever
Echo virus infection	Encephalitis Japanese B	Endocarditis rheumatic
Echovirus test	Encephalitis lethargica	Endocarditis staphylococcal
Echovirus test positive	Encephalitis meningococcal	Endocarditis syphilitic
Ecthyma	Encephalitis mumps	Endocarditis viral
Eczema herpeticum	Encephalitis post immunisation	Endometritis
Eczema impetiginous	Encephalitis post varicella	Endometritis bacterial
Eczema infected	Encephalitis protozoal	Endometritis decidual
Eczema vaccinatum	Encephalitis rickettsial	Endometritis gonococcal
Ehrlichia test	Encephalitis toxic	Endophthalmitis
Ehrlichia test positive	Encephalitis venezuelan equine	Endotoxaemia
Elephantiasis nostras verrucosa	Encephalitis viral	Endotoxic shock
Embolic pneumonia	Encephalitis western equine	Enteritis infectious
Empedobacter brevis infection	Encephalomyelitis	Enteritis necroticans
Empedobacter test positive	Encephalomyelitis rubella	Enterobacter bacteraemia
Emphysematous cholecystitis	End stage AIDS	Enterobacter infection
Emphysematous cystitis	Endemic syphilis	Enterobacter pneumonia
Emphysematous pyelonephritis	Endocarditis	Enterobacter sepsis
Empyema	Endocarditis bacterial	Enterobacter test positive
Encephalitis	Endocarditis candida	Enterobacter tracheobronchitis
Encephalitis allergic		
Encephalitis australia		

Enterobiasis	Epiglottitis obstructive	Escherichia urinary tract infection
Enterococcal bacteraemia	Epstein-Barr viraemia	Escherichia vaginitis
Enterococcal infection	Epstein-Barr virus antibody	Eubacterium infection
Enterococcal sepsis	Epstein-Barr virus antibody positive	Exanthema subitum
Enterococcus test positive	Epstein-Barr virus antigen positive	Exserohilum infection
Enterocolitis AIDS	Epstein-Barr virus associated lymphoma	External ear cellulitis
Enterocolitis bacterial	Epstein-Barr virus associated lymphoproliferative disorder	Extradural abscess
Enterocolitis fungal	Epstein-Barr virus infection	Extrapulmonary tuberculosis
Enterocolitis helminthic	Epstein-Barr virus test	Eye abscess
Enterocolitis infectious	Epstein-Barr virus test positive	Eye infection
Enterocolitis viral	Erosive balanitis	Eye infection bacterial
Enterovirus infection	Eruptive pseudoangiomatosis	Eye infection chlamydial
Enterovirus test	Erysipelas	Eye infection fungal
Enterovirus test positive	Erysipeloid	Eye infection gonococcal
Eosinophilia myalgia syndrome	Erysipelothrix infection	Eye infection helminthic
Eosinophilic cystitis	Erysipelothrix test positive	Eye infection intraocular
Ependymitis	Erythema induratum	Eye infection staphylococcal
Epidemic pleurodynia	Erythema infectiosum	Eye infection syphilitic
Epidemic polyarthritits	Erythema migrans	Eye infection toxoplasmal
Epidemic typhus	Erythrasma	Eye infection viral
Epidermodysplasia verruciformis	Escherichia bacteraemia	Eyelid boil
Epididymitis	Escherichia infection	Eyelid folliculitis
Epididymitis blastomyces	Escherichia pyelonephritis	Eyelid infection
Epididymitis mumps	Escherichia sepsis	Faecal-oral transmission of infection
Epididymitis tuberculous	Escherichia test positive	Fallopian tube abscess
Epididymitis ureaplasmal		Fascial infection
Epididymo-orchitis gonococcal		Fascioliasis
Epiglottitis		Fasciolopsiasis
Epiglottitis haemophilus		Febrile infection

Female genital tract tuberculosis	Funisitis	Gastroenteritis cryptococcal
Femoral hernia gangrenous	Furuncle	Gastroenteritis cryptosporidial
Filariasis	Fusarium infection	Gastroenteritis
Filariasis lymphatic	Fusobacterium infection	enteroviral
Filovirus infection	Fusobacterium test positive	Gastroenteritis
Filovirus test positive	Gallbladder abscess	Escherichia coli
Flavivirus infection	Gallbladder empyema	Gastroenteritis norovirus
